**5.4.4 Final Study Visit (Study Visit 3)**

At 180 (+/- 14) days post discharge, all participants will have a routine clinic visit. The visit will include an assessment of current medication use and doses, physical examination including heart rate assessment (by exam and 1 ECG), and systolic blood pressure. The final dose of ivabradine prior to the visit will be recorded. Participants never initiated on or eligible for ivabradine will also be recorded. The study investigators or designee will assess quality of life (KCCQ and PGA).

Using the study schedule of assessments, provider-determined heart rate will be assessed at the following time points: baseline, post-discharge clinical follow-up visit (within 7-14

PRIME-HF

---

days of hospital discharge), week 6, and day 180. Patient quality of life assessment will be assessed at the following time points: baseline, post-discharge clinical follow-up visit (within 7-14 days of hospital discharge), week 6, and day 180.

PRIME-HF

---

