### 2.5.3 Tertiary endpoints

Tertiary endpoints are

- 1) Beta-blocker use at 180 days as assessed by the:
  - a) Proportion of participants on beta-blocker at 180 days
  - b) Proportion on target dose
  - c) Proportion discontinuing beta-blockers at 180 days and
  - d.) Mean change in beta-blocker dose from discharge to 180 days.
- 2). Ivabradine use at 180 days as assessed by the:
  - a) Proportion of appropriate participants with any initiation of ivabradine at 180 days
  - b) Proportion of appropriate participants at the maximum dose of ivabradine at 180 day.
  - c) Mean dose of ivabradine achieved at 180 days.
- 3). Tolerability of ivabradine and events of interest:
  - a) Symptomatic bradycardia
  - b) Symptomatic hypotension
  - c) Other symptoms leading to ivabradine discontinuation
- 4). Summary of barriers to acquisition of ivabradine

---

 Beta-blocker target dose is defined as participants who receive Carvedilol equivalent total daily dose of 50 mg

 Appropriate participants are defined as participants who have a sinus rhythm (participants excluding those with AF) and heart rate of  $\geq 70$  bpm. For participants missing 180 day ECG, results from the baseline ECG are used to determine appropriateness.

 Receiving ivabradine at any time point during the study.

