### 9.3 Tertiary Analyses

1. Beta-blocker use at 180 days as assessed by the (a) proportion of participants on a beta-blocker at 180-days, (b) proportion on target dose, (c) proportion of participants who are at  $\geq 50\%$  target dose (d) the proportion discontinuing beta-blockers at 180 days and (e) the mean change in beta-blocker dose from discharge to 180 days will be compared between the randomization arms. - The mean change of beta-blocker dose will be calculated for participants who provide data at baseline and at 180 days post-discharge visits.

The proportions of participants on beta-blocker, the proportions on target dose, the proportion on at least 50% of the target dose, and the proportions discontinuing beta-blocker at 180 days will be summarized by randomization arms and tested using the Chi-square test. The change in beta-blocker dose from discharge to 180 days will be summarized and compared using the Wilcoxon rank sum test.

2. Ivabradine use at 180 days as assessed by the (a) proportion of appropriate participants with any initiation of ivabradine at 180 days, (b) the proportion of appropriate participants at the maximum dose of ivabradine at 180 day (i.e., 7.5 mg

---

 Comparing the mean change in beta-blocker dose is interpreted as comparing the distribution of dose changes between the randomization arms.

twice daily), and (c) the mean dose of ivabradine achieved at 180 days will be compared between the randomization arms.

Participants who do not provide the 180 day visit data will be coded as failures (ivabradine=0 and dosage=0.0). The mean dose of ivabradine achieved will be calculated for participants who provide data at 180 days post-discharge visit and using imputed values for the participants who do not provide 180 day visit data. As a sensitivity analysis, data will also be analyzed on observed data without imputing missing values. In addition, ivabradine dosage will be summarized for participants on ivabradine at the 180 day visit.

The proportions of appropriate participants with any initiation of ivabradine and the proportion of appropriate participants at the maximum dose of ivabradine at 180 days will be summarized as incidences by the randomization arms and tested using the Chi-Square test. The dose of ivabradine achieved at 180 days will be summarized and compared using the Wilcoxon rank sum test.

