### Data Sources for Endpoints

#### 1. Ivabradine use

a) Ivabradine use (1/0) at 180 days comes from either the current medications data (CM) or the ivabradine usage data (DRG).

If CM.CMIVA=1 and VISITID=50 or DRG.DRIVA=1 and VISITID=50. If missing then it is imputed to 0. (Note: analysis will also be done without imputation).

b) Ivabradine dose change from baseline to 180 days

Ivabradine use and dose at baseline comes from the ivabradine initiation in hospital (EXH) data EXH.EXRECH (use) and EXH.EXLDH (dose) EXH.EXRECH (use) and EXH.EXLDH (dose) (VISITID=10) and ivabradine obtaining the first time (outpatient) (EX) EX.EXREC and EX.EXPDOS (VISITID=60 study wide to be merged in)

For other time points use the ivabradine usage data DRG.DRIVA (use) DRG.DRDSG (dose). Missing doses will be imputed to 0. (Note: analysis will also be done without imputation).

Dose change from baseline to 180 days = EXH.EXLDH, EX.EXDOS (VISITID=10)-DRG.DRDSG (where VISITID=50)

c) Proportion with any initiation

If participant received ivabradine at any time during the visits

If EXH.EXRECH=1 or EX.EXREC=1 or CM.CMIVA=1 or DRG.DRIVA=1 at any visit then ANYIVA=1 else ANYIVA=0; (Note: No imputation of missing ivabradine use occurs for this derivation)

d) Proportion on maximum dose at 180 days

Use ivabradine usage data

If DRG.DRSG =15 (mg) and VISITID=50 then on ivabradine maximum dose=1; else if DRG.DRSG not missing on ivabradine maximum dose=0.

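### SAP Appendix 1 scores maximum dose at day 180 from a dose field without requiring current ivabradine use, and the documents do not say what that field holds after a participant stops

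*SAP*

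**What the plan says.** SAP 2.5.3 lists two dose endpoints under tertiary endpoint 2: the share of appropriate participants at the maximum dose at day 180 (2(b)) and "Mean dose of ivabradine achieved at 180 days" (2(c)).

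Appendix 1 item 1(d) derives 2(b) in two branches: "If DRG.DRSG =15 (mg) and VISITID=50 then on ivabradine maximum dose=1", and "else if DRG.DRSG not missing on ivabradine maximum dose=0". The value 15 mg is the daily total of 7.5 mg twice daily. No use flag appears in either branch.

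Other items in the same appendix section do rely on use flags. Item 1(a), the primary endpoint, reads: "If CM.CMIVA=1 and VISITID=50 or DRG.DRIVA=1 and VISITID=50. If missing then it is imputed to 0". Item 1(c), any initiation, is also built from use flags. Item 1(b), dose change from baseline, names use and dose as separate fields of the ivabradine usage data and sets missing doses to 0. It spells the dose field DRDSG, where item 1(d) has DRSG.

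SAP 9.3 item 2 gives dose 0 to participants who supply no day-180 visit data. It adds that "ivabradine dosage will be summarized for participants on ivabradine at the 180 day visit".

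Protocol 5.4.4 asks sites for two dose items at the last visit: "The visit will include an assessment of current medication use and doses, physical examination including heart rate assessment", and then "The final dose of ivabradine prior to the visit will be recorded".

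**The concern.** A dose at day 180 should be zero for anyone no longer taking the drug. Item 1(d) secures this only if the data happen to hold a zero. The protocol's request for the last dose before the visit can be answered for anyone who ever started, including someone who stopped weeks earlier. Protocol 7.4 also asks that final-visit activities be done when treatment is discontinued early, when the last dose taken is the natural entry. So the visit-50 field could plausibly hold a positive dose for a non-user.

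If it does, one person can be a failure on the primary endpoint and a success on the maximum-dose endpoint. If the field is blank instead, non-users drop out of the proportion, which becomes a proportion among users and no longer a comparison of the randomized groups.

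**Working it through.** **No plan figure to reproduce.** The documents give no expected rate for maximum dose or for stopping. The check is therefore a trace of the rules, followed by an illustration on assumed counts.

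**Rule trace.** Take a participant seen at day 180 with both use flags equal to 0.

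| Visit-50 dose field | Primary, item 1(a) | Maximum dose, item 1(d) as written | Maximum dose if current use is required |
|---|---|---|---|
| Last dose kept, 15 mg | 0 | 1 | 0 |
| Explicit 0 | 0 | 0 | 0 |
| Blank | 0 | not scored | 0 |

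The blank row becomes 0 only if the missing-dose rule of item 1(b) is run first, which item 1(d) does not say. The zero-dose rule in SAP 9.3 item 2 does not help in the first row, because it covers only people without day-180 visit data. Nor does item 1(b), because the dose is not missing.

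**If the last dose is kept.** Let m be the true maximum-dose count in an arm, s the number of non-users with a retained 15 mg, and n the arm size.

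- Observed proportion = (m + s)/n.
- Error in the arm difference = s(pre-discharge)/n − s(usual care)/n, taking equal arms. Its sign depends on the two values of s, which the documents do not give.
- SAP 2.3 gives 104 enrolled. An assumed even split gives n = 52, so one such record moves an arm by 1/52 = 1.9 points.

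Illustration by the planned chi-square test, uncorrected, with all counts assumed (pre-discharge / usual care):

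| True count | Retained 15 mg | Observed | p |
|---|---|---|---|
| 10 / 5 | 0 / 0 | 19.2% / 9.6% | 0.16 |
| 10 / 5 | 2 / 0 | 23.1% / 9.6% | 0.06 |
| 10 / 5 | 4 / 1 | 26.9% / 11.5% | 0.047 |
| 10 / 5 | 8 / 2 | 34.6% / 13.5% | 0.01 |
| 13 / 9 | 0 / 0 | 25.0% / 17.3% | 0.34 |
| 13 / 9 | 4 / 1 | 32.7% / 19.2% | 0.12 |

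These rows assume more retained records in the pre-discharge arm. Equal numbers would leave the difference in points unchanged, and more in usual care would shrink it.

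**If the field is blank for every non-user.** Take the use rates assumed in SAP 2.3, 50% and 35%.

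- Users: 0.50 × 52 = 26, and 0.35 × 52 = 18.2, about 18.
- With the same 10 and 5 at maximum dose, and a dose recorded for every user, item 1(d) gives 10/26 = 38.5% and 5/18 = 27.8%.
- Over all participants the figures are 10/52 = 19.2% and 5/52 = 9.6%.

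**Mean dose.** Appendix 1 has no derivation for endpoint 2(c); item 1(b) is dose change. If 2(c) uses the same visit-50 field, each retained 15 mg adds 15/52 = 0.29 mg/day to the arm mean, and lower retained doses add proportionately less.

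**Limit of the illustration.** Endpoint 2(b) applies to appropriate participants: sinus rhythm and heart rate at least 70 bpm, judged on the day-180 ECG or, if that is missing, the baseline ECG. That denominator can only be the same or smaller, so one record would move it by at least 1.9 points. Its size is not given.

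**The case against.** The strongest reply is that no document links the visit-50 dose field to the protocol's last-dose item. The same protocol section also asks for current medication doses. The usage dataset is filled at every follow-up contact, and at the contacts before the last the protocol asks only for current use and doses. A repeated form that pairs use with dose may well hold the current dose throughout, with 0 entered for non-users. In that case the rule gives the right answer. Only tertiary endpoints, described as exploratory, are involved.

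Most of this stands. A reader might infer that the SAP does score the last-dose item, that the dose results are therefore overstated, and that the error flatters pre-discharge initiation. The documents support none of these. The content of the field is not stated, no discontinuation rates are given by arm, and the error is zero if the field holds 0. A reader might also take the users-only dose summary in SAP 9.3 as proof that stopped participants carry positive doses in the main analysis. It is not proof: that analysis already includes zero-dose participants by design, and a users-only summary is its natural complement.

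The reply does not rescue the rule as written. Even a current-dose field may be left blank for non-users, and item 1(d) then drops them.

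**Conclusion.** The gap is real but limited. Item 1(d) is correct for non-users only under a data-entry convention that neither document states, namely an explicit 0. A retained 15 mg produces a false maximum-dose success. A blank produces an unscored participant, which conflicts with the coding of missing doses as 0 in item 1(b) and of participants without day-180 data as dose 0 in SAP 9.3 item 2.

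Misclassification is possible, not shown. The size and direction of any arm difference cannot be determined from the documents. The 1.9 points per record rests on an assumed 52 per arm, and every count in the illustration is assumed. The primary and secondary endpoints are unaffected. Tertiary endpoint 2(b) is exposed, and 2(c) only if it uses the same field.

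**What to change.** In Appendix 1 item 1(d), and in a stated derivation of day-180 mean dose under SAP 9.3 item 2, use the visit-50 dose only when day-180 ivabradine use is 1 by the item 1(a) derivation. Otherwise set dose to 0 and maximum dose to 0. Keep the planned analysis on observed data, in which a participant seen at day 180 and recorded as not using counts as an observed zero. State what the dose field holds after stopping, and use one spelling of its name. Report the last dose before stopping separately if wanted.

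A cross-tabulation of the visit-50 dose field (blank, 0, positive) against day-180 use, by arm, would show at once whether any record is affected. SAP section 1 provides the supplement or amendment route. Addendum 2 shows that the database has been locked and treatment unblinded, so a change made now should be labelled as such, with results by both rules.

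The cost is one added condition. The dose figures may become slightly less favourable.

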### **13.5 Handling of Missing Data**

All efforts will be made to make sure all data needed for the analyses outlined in the SAP are complete. However, it is possible that some data will be missing. Missing data is a common problem in clinical research. It reduces statistical power (the probability that the test will reject the null hypothesis when it is false) and results in biased parameter estimates (Kang, 2013). Outcomes for participants who do not provide data during the 180 day visit will be imputed as failures. Missing heart rate, PGA and KCCQ values will be imputed for the final (180 day) visit using multiple imputation technique if more than 10% of the measures are missing.

It is expected that missing 180 day visit values constitute > 10% of the secondary endpoints (Heart rate, KCCQ and PGA). Thus, multiple imputation (MI) will be performed and presented for the ITT and Treated populations, respectively.

Imputation will be conducted using PROC MI and imputed data analyzed with PROC MIANALYZE in SAS 9.4.

The following variables shall be used in the imputation:

AGE, SEX, RACE, ETHNICITY, WEIGHT, NYHA class, LVEF, and baseline value of the imputed variable) – For NYHA class, WEIGHT and LVEF, baseline values will be used.

RACE shall be recoded to: White, Black and Others (combining American Indian, other, and mixed - as they are of very low frequency)

Results of the imputation shall be presented as the primary result of the secondary endpoints. A total of 25 imputations will be conducted for each imputed value.

Sensitivity analyses will be conducted by analyzing these endpoints with and without imputation.

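### The SAP's derivation of the tertiary maximum-dose proportion leaves a missing day-180 dose unclassified, whereas sections 9.3 and 13.5 count participants without day-180 data as failures

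*SAP*

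**What the plan says.** SAP section 2.5.3 lists the endpoint as "Proportion of appropriate participants at the maximum dose of ivabradine at 180 day". Its footnote defines appropriate as sinus rhythm with a heart rate of at least 70 bpm, and falls back on the baseline ECG when the 180-day ECG is missing.

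Section 9.3 item 2 covers three measures together: any initiation, maximum dose and mean dose. For these it says "Participants who do not provide the 180 day visit data will be coded as failures (ivabradine=0 and dosage=0.0"). It makes the analysis of observed data without imputation a sensitivity analysis, and it adds a separate dosage summary for participants on drug at day 180. Section 13.5 gives the same rule in general form: "Outcomes for participants who do not provide data during the 180 day visit will be imputed as failures".

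The derivation is in Appendix 1, item 1(d). It reads "If DRG.DRSG =15 (mg) and VISITID=50 then on ivabradine maximum dose=1", followed by "else if DRG.DRSG not missing on ivabradine maximum dose=0". It has no branch for a missing dose and no imputation sentence. Section 13.2 sets the default that percentages are taken over non-missing values unless stated otherwise.

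The neighbouring items do address imputation. Item 1(a) imputes missing use to 0. Item 1(b), on dose change, says "Missing doses will be imputed to 0". Item 1(c), on any initiation, says "No imputation of missing ivabradine use occurs for this derivation". Item 1(b) names the dose variable DRG.DRDSG, and item 1(d) names it DRG.DRSG.

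**The concern.** A programmer who codes 1(d) as written produces the observed-data version of the endpoint, which 9.3 reserves for sensitivity analysis. The version that 9.3 wants as the main result then has no derivation.

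What is at stake depends on who has a blank dose at day 180. Participants with no day-180 visit are the certain case. Under 9.3 they are failures, and under literal 1(d) they vanish. They are not a remote possibility, because section 13.5 expects more than 10% of day-180 values to be missing for heart rate, KCCQ and PGA.

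The second group is attenders who are off ivabradine. If their dose field is blank rather than 0, they leave too, and the comparison is then restricted to people still taking the drug. Use at 180 days is the primary outcome and is expected to differ between arms, so this would compare post-randomisation subsets selected on the very outcome that the strategy is meant to change. A strategy that puts more people on the drug, and hence more on the maximum dose, could show no difference.

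**Working it through.** **1. The rules side by side.**

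| Participant at day 180 (appropriate) | Sections 9.3 / 13.5 | Appendix 1(d), literal, with 13.2 |
|---|---|---|
| Recorded 15 mg daily | 1 | 1 |
| Recorded lower dose, or recorded 0 | 0 | 0 |
| No day-180 visit data, dose blank | 0 (failure, dose 0.0) | no value, out of the denominator |
| Attended, off drug, dose blank | 0 if item 1(b)'s imputation is applied; not covered by the 9.3 sentence | no value, out of the denominator |

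The third row is a conflict whatever the coding convention for off-drug attenders. The baseline-ECG fallback in 2.5.3 sharpens it. Entry requires sinus rhythm and a heart rate of at least 70 bpm (protocol section 3.2), so a participant with no day-180 ECG will ordinarily count as appropriate. The plan therefore places that person in the denominator, and 1(d) takes the person out again.

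**2. The plan's own figures.** No figure is given for the maximum-dose endpoint. The only use rates in the documents are the planning rates of 35% and 50% (protocol 10.2, SAP 2.3). They reproduce the stated sample size: the continuity-corrected two-proportion formula at two-sided 0.05 and 85% power gives 207 per arm, 414 in total, and 414 / 0.92 = 450.

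**3. Illustration.** Inputs and their status:
- N = 52 per arm: the 104 enrolled (SAP 2.3), with an even split assumed.
- All 52 counted as appropriate: assumed.
- Use u = 50% pre-discharge and 35% usual care: the planning assumption.
- q, the share of users at maximum dose: assumed.
- f, the share of participants not on drug who have a recorded 0: assumed, because the documents do not show it.

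Formula: proportion = N·u·q / [N·u + f·N·(1 − u)]. With f = 1 this is u·q, which is the failure-coded result. With f = 0 it is q, so the use rate cancels.

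Users: 52 × 0.50 = 26 and 52 × 0.35 = 18.2. Others: 26 and 33.8.

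| q (pre-discharge, usual care) | f = 1 (same as failure coding) | f = 0.5 | f = 0 (all blank) |
|---|---|---|---|
| 20%, 20% | 10.0% vs 7.0% | 13.3% vs 10.4% | 20% vs 20% |
| 40%, 40% | 20.0% vs 14.0% | 26.7% vs 20.7% | 40% vs 40% |
| 60%, 60% | 30.0% vs 21.0% | 40.0% vs 31.1% | 60% vs 60% |
| 40%, 50% | 20.0% vs 17.5% | 26.7% vs 25.9% | 40% vs 50% |

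Worked cell, q = 40%, f = 0.5: pre-discharge 10.4 / (26 + 13) = 26.7%; usual care 7.28 / (18.2 + 16.9) = 20.7%.

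**4. Reading the table.** With equal q, the all-blank case removes an arm difference of 3 to 9 points. With q of 40% vs 50%, the difference goes from +2.5 to −10 points. With half of the non-user doses recorded as 0 and equal q, the levels rise but the difference hardly moves (for q = 40%, 5.9 points against 6.0).

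**5. Significance at the planning rates.** With q = 40% and counts rounded, failure coding gives 10/52 vs 7/52 (Fisher p = 0.60) and users only gives 10/26 vs 7/18 (p = 1.0). Section 9.3 plans a chi-square test; Fisher is used here only as a check. Neither version is significant.

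**The case against.** The strongest reply is that imputation comes first. Item 1(d) draws on the ivabradine usage data, the same source for which 1(b) sets missing doses to 0. Item 1(c) opts out of imputation expressly and 1(d) does not. Section 13.5 applies failure coding to day-180 outcomes generally, and 9.3 could count as the exception that 13.2 allows. If all this runs before 1(d), no dose is missing and 1(d) agrees with 9.3. On that view the fault is only an unstated order of steps.

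This reading is possible but does not settle the matter. It makes the non-missing condition in 1(d) redundant. The order is nowhere stated. The imputation sentence in 1(b) belongs to the dose-change measure and to a differently named variable. A programmer could reasonably code either version.

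Other parts of the reply stand and limit the point:
- A reader might infer that an all-participant proportion is turned into one among users. The planned denominator is "the proportion of appropriate participants at the maximum dose of ivabradine at 180 day", so it was never all participants. A users-only result needs blank dose fields for everyone off drug, and no case report form or data dictionary in the documents shows that.
- A reader might infer that the two rules give opposite conclusions. Counts can be chosen to do that for significance: 25 users with 10 at maximum against 6 users with 2 at maximum, of 52 each, gives p = 0.03 with failure coding (10/52 vs 2/52) and p = 1.0 among users (10/25 vs 2/6). But 6/52 is 11.5% use under usual care, far from the planned 35%, and both versions still favour pre-discharge initiation.
- The measure is one component of an exploratory tertiary endpoint.

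**Conclusion.** The point holds in limited form. Item 1(d), read literally with 13.2, excludes participants with a missing day-180 dose, while 9.3 item 2 and 13.5 count participants without day-180 data as failures. The literal text yields the planned sensitivity analysis in place of the main one.

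The size is uncertain because it depends on how the dose field is filled for people off drug. It runs from nil, if every participant not on drug has a recorded 0, to complete loss of the arm difference, if all such doses are blank and equal shares of users reach the maximum dose. A sign reversal needs the further assumption that a larger share of usual-care users are at maximum dose. All of these results rest on the assumed even split, on everyone being appropriate and on the planning use rates; none is a trial result.

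The primary analysis has its own explicit failure coding (section 9.1 and Appendix item 1(a)), so it and the sample size are unaffected. The correction should be made, because the ambiguity concerns which version is reported as the main result for this endpoint.

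**What to change.** In Appendix 1, item 1(d):
- State that, among appropriate participants, non-use and a missing day-180 dose are set to 0 before the derivation, so that maximum dose = 0 for them in the main analysis.
- Keep the present non-missing version, labelled as the observed-data sensitivity analysis of 9.3.
- Use one variable name for the day-180 dose in 1(b) and 1(d) (DRG.DRDSG or DRG.DRSG, whichever the database holds).

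The cost is about one line of derivation text and the matching program change. No new data are needed. Section 103's rule on changes need not be stretched: under SAP section 1, an addition of this kind goes into a supplement if judged non-substantive and an amendment if substantive. If results have already been produced, check which version was run and label it accordingly.
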